9.15 Adverse Events and Adverse Reactions

Adverse Event:

An AE is "any untoward medical occurrence in a subject or clinical investigation subject administered a pharmaceutical product and which does not necessarily have a causal relationship with this treatment (International Conference on Harmonisation [ICH] E2A)." Study drug includes both the investigational drug under evaluation and the comparator drug or placebo. Medical conditions that were present before starting study drug are only considered AEs if they worsen after the subject has started the study drug.

Adverse Drug Reaction:

In the pre-approval clinical experience with a new medicinal product: "all noxious and unintended responses to a medicinal product related to any dose should be considered an Adverse Drug Reaction (ADR)." The phrase "responses to a medical product" means that a causal relationship between a medical product and an AE is at least a reasonable possibility, i.e., the relations cannot be ruled out.

Unexpected Adverse Drug Reaction:

An unexpected ADR is an ADR, the nature or severity of which is not consistent with the applicable product information (e.g., Investigator's Brochure for an unapproved investigational medicinal product).

9.15.1 Serious Adverse Event (SAE)

A SAE is any event that meets any of the following criteria:

- Death
- Life-threatening
- Inpatient hospitalization or prolongation of existing hospitalization
- Persistent or significant disability/incapacity
- Congenital anomaly/birth defect in the offspring of a subject

- Other: Important medical events that may not result in death, be life-threatening, or require
 hospitalization, may be considered an SAE when, based upon appropriate medical judgment,
 they may jeopardize the subject and may require medical or surgical intervention to prevent
 one of the outcomes listed in this definition. Examples of such events are:
 - Intensive treatment in an emergency room or at home for allergic bronchospasm
 - Blood dyscrasias or convulsions that do not result in inpatient hospitalization
 - Development of drug dependency or drug abuse

A Suspected Unexpected Serious Adverse Reaction (SUSAR) is referred to an ADR that complies with both the definitions of "serious" and "unexpected."

Any abnormal laboratory test results felt to be clinically significant in the medical and scientific judgment of the Investigator are to be recorded as AEs or SAEs. Subject's hematological parameters, in particular platelet counts, should be carefully monitored. Subjects should further be carefully monitored for signs of gastrointestinal AE's and, if necessary.

9.15.2 Recording of Adverse Events

AEs will be recorded and evaluated for their seriousness, severity, and relationship to the study medication. Adverse events will be collected and documented during the course of the study, from ICF signature until a period of 12±2 days following the last study drug administration.

Adverse events will be followed-up until complete resolution, or until the Investigator judges it to be safe to discontinue follow-up. The relationship to the study medication will be classified by the Investigator according section 9.15.4.

9.15.3 Assessment of Severity

The severity of AEs will be assessed and graded according to the most recently published National Cancer Institute Common Terminology Criteria for AE (CTCAE).

9.15.4 Assessment of Relationship to the Study Drug

The relationship with the study drug should be assessed as:

- related to study drug;
- not related to study drug;
- unknown.

The assessment of the relationship of an adverse event with the administration of study drug is a clinical decision based on all available information at the time of the completion of the CRF.

 An assessment of "Related" indicates that there is a reasonable suspicion that the AE is associated with the use of the study drug.

- An assessment of "Not related" would include the existence of a clear alternative explanation, or non-plausibility.
- An assessment "Unknown" indicates there is not a reasonable suspicion that the AE is
 associated with the use of the study drug and at the same time there is not the existence of
 a clear alternative explanation or non-plausibility. In this case, Investigator has to collect
 all possible information in order to assess the relationship with the study drug,
 particularly in case of SAEs.

9.15.5 Serious Adverse Events Reporting

Any SAE that occurs after a subject has signed the Informed Consent Form must be reported by the Investigator to the Sponsor within 24 hours of learning of its occurrence.

The Investigator must notify the Sponsor of the SAE by completing the word version of the SAE reporting form and e-mailing the pdf version to the addresses specified below.

Serious adverse event reports must be made whether or not the Investigator considers the event to be related to the investigational drug.

The Investigators are required to complete the SAE Form. Sufficient details must be provided to allow for a complete medical assessment of the SAE and independent determination of possible causality. The Investigators are obliged to pursue and provide additional information as requested by Italfarmaco S.p.A. or its designee. The notification must be directed to:

Italfarmaco S.p.A.

Corporate Drug Safety
[name]
[name]
Phone: PPD
Fax: PPD
Fax (back-up): PPD
Mobile: PPD
e-mail: [contact]

The same procedure must be applied to the SAE follow-up information.

9.15.6 Suspected, Unexpected, Serious Adverse Drug Reactions

9.15.6.1 Fatal or Life-threatening Serious, Unexpected Adverse Drug Reactions

The Sponsor is responsible for notifying regulatory agencies of fatal or life-threatening serious, unexpected adverse drug reactions (by telephone, facsimile transmission or in writing) as soon as possible, but no later than 7 calendar days after becoming aware of the information. Additionally, within 8 days after having informed the agency(ies), a complete report must be submitted, including an assessment of the importance and implication of any findings. Syneos Health will handle notifications to the Canadian regulatory agency on behalf of the Sponsor.

It is the responsibility of the clinical site to report as soon as possible, but no later than 7 calendar days after first knowledge by the Investigator, fatal or life-threatening serious, unexpected adverse drug reactions to the IEC responsible for the study.

9.15.6.2 Other Suspected, Unexpected, Serious Adverse Drug Reactions

The Sponsor is responsible for notifying regulatory agencies of all other suspected, unexpected, serious adverse drug reactions that are neither fatal nor life-threatening as soon as possible, but no later than 15 calendar days after becoming aware of the information. Syneos Health will handle notifications to the Canadian regulatory agency on behalf of the Sponsor.

It is the responsibility of the clinical site to report to the IEC responsible for the study all other suspected, unexpected, serious adverse drug reactions that are neither fatal nor life-threatening, as soon as possible, but no later than 15 calendar days after first knowledge by the Investigator.

9.15.7 Adverse Events of Special Interest

AESI are required to be reported by the investigator to the Sponsor immediately (i.e., no more than 24 hours after learning of the event). AESI for this study include the following:

- Torsade de pointes
- Sudden death
- Ventricular tachycardia
- Ventricular fibrillation and flutter
- Post-dose syncope
- Seizures

Which are to be classified as AESI in the CRF and will be recorded from ICF signature and throughout the study period until study completion (follow-up telephone call). When these events are identified they should be examined closely for other risks factors, and evaluation and the need for evaluation by a cardiac specialist will be discussed by the Investigator and the Sponsor

9.16 Pregnancy

In the event a dosed female subject (or the female partner of a dosed male subject, when applicable) becomes pregnant during the treatment phase or through 3 months after the last dose of study drug, this pregnancy must be reported to the site personnel immediately.

The Investigator is required to report within 24 hours the pregnancy, using the Pregnancy Notification Form, to Italfarmaco Corporate Drug Safety by mailing to the following e-mail address:

Italfarmaco Corporate Drug Safety: [contact]

If notification cannot be made via these means due to technical delivery problems, initial notification may be made by telephone or by fax, using the following numbers:

Italfarmaco Corporate Drug Safety:
Phone: PPD
Fax: PPD
Fax (back-up): PPD

Follow-up information regarding the course and outcome of the pregnancy with an onset within the above defined time frame, will be documented (after obtaining the consent of the female partner, when applicable) as per site's SOP. Any premature termination should be reported, and the status of the mother and child should be reported to the sponsor after delivery. If the outcome of the pregnancy meets the criteria for classification as an SAE, reporting of the event to the IEC and regulatory agency(ies) will be performed as per site's SOP.

Any subject who becomes pregnant during the study will be immediately withdrawn.

9.17 Overdose

In general, a drug overdose in a clinical study is defined as the accidental or intentional use of a drug or medicine in an amount exceeding the protocol defined dose. The Investigator must immediately notify the Sponsor of any occurrence of overdose with study drug.

Any overdose or incorrect administration of study drug should be recorded in the CTMS and reported on the relevant study drug administration Case Report Form (CRF) and the Protocol Deviation CRF. AEs associated with an overdose or incorrect administration of study drug should be reported on the relevant Adverse Event CRF. No safety data related to overdosing of ITF2357 are available.

Any instance of overdose (suspected or confirmed, with and without an AE) must be reported to the Sponsor within 24 hours and, only in case of AEs, it must be fully documented as a SAE. Details of any signs or symptoms and their management should be recorded in the SAE Form including details of any antidote or systematic treatment administered. Any signs or symptoms of over-dosage will be treated symptomatically.

Any other situations putting the subject at risk of an adverse reaction, such as misuse and abuse, medication errors, suspect of transmission of infective agents must be reported to the Sponsor within 24 hours and be fully documented as a SAE.

MedDRA for coding event and WHO Drug Dictionary for coding concomitant medications will be used within the Italfarmaco safety database.

9.18 Reportable Disease

In the case a subject has or manifests any clinical signs characteristic of a reportable disease or condition (e.g., HIV, tuberculosis, SARS), it is the responsibility of the Qualified Investigator or designee to notify the Public Health authorities within 48 hours after becoming aware of the information.

9.19 Premature Termination of the Study

The study may be prematurely terminated by the Qualified Investigator following consultation with the Sponsor, by the Sponsor or by the regulatory authorities. Following a decision to discontinue the trial, the Qualified Investigator or designee will promptly inform the active study subjects and the IEC responsible for this trial, stating the reasons for discontinuation of the study and, furthermore, advise them in writing of any potential risks to the health of study subjects or other persons. It is the Sponsor's responsibility to report the premature termination of the study to the regulatory authority(ies), when required by the applicable regulatory requirement(s). The Canadian regulatory agency must be informed of premature termination within 15 days, provided with the reasons for the trial discontinuation and of any potential risks to the health of study subjects or other persons. Syneos Health may notify the Canadian regulatory agency on behalf of the Sponsor upon his request.

10. Analytical Methodology

When applicable, samples will be transported to the bioanalytical facility in at least two separate shipments, with each set of aliquots in separate shipments. Once the bioanalytical laboratory confirms receipt of the first shipment, the second set of aliquots may be sent. The samples should be packed on sufficient dry ice to keep them frozen for at least 72 hours.

The Bioanalytical Division of Syneos Health will analyze ITF2357, ITF2374, ITF2375, ITF2440, ITF2563, and ITF2955 glucuronide, in plasma and urine samples, and moxifloxacin in plasma samples using validated methods.

Analyst and Watson LIMS (Laboratory Information Management System) will be used at different steps of the analysis.

The bioanalytical work in support of the study will be conducted in compliance with the GCP, using the SOPs in place in the Bioanalytical Division of Syneos Health. These SOPs are in accordance with applicable regulations in the industry: Guidelines on Bioanalytical Method Validation, Good Laboratory Practice (GLP), and Guideline for GCP ICH E6 (R2).

Samples from subjects included in the Pharmacokinetic Population (see section 12.3.3) and from subjects who were withdrawn from the study due to adverse events, or vomiting episodes, will be analyzed.

11. Study Endpoints

Primary endpoint:

 The primary endpoint for the cardiodynamic ECG assessment is the placebo-corrected change from-baseline QTcF (ΔΔQTcF).

Secondary endpoints:

 Change-from-baseline QTcF, PR, QRS, and heart rate (HR) (ΔQTcF, ΔPR, ΔQRS, and ΔHR)

- Placebo-corrected ΔPR, ΔQRS and ΔHR (ΔΔPR, ΔΔQRS, and ΔΔHR)
- Categorical outliers for QTcF, HR, PR, and QRS
- Frequency of treatment emergent changes of T-wave morphology and U-wave presence
- The PK endpoints will include the plasma and urine PK parameters for ITF2357, ITF2374, ITF2375, ITF2440, ITF2563, ITF2955 glucuronide, and moxifloxacin (as described in the Pharmacokinetics section).
- Safety and tolerability to ITF2357 will be evaluated through the assessment of adverse
 events (i.e., seriousness, severity, relationship to the study medication, outcome, duration,
 and management), vital signs, ECG, and clinical laboratory parameters.

12. Pharmacokinetic and Statistical Analyses

Pharmacokinetic analysis will be performed using Phoenix® WinNonlin®. Inferential statistical analyses will be performed using SAS® according to FDA and EMA guidelines.

12.1 Plasma PK Parameters

The following pharmacokinetic parameters will be calculated by standard non-compartmental methods for ITF2357 and metabolites: ITF2374, ITF2375, ITF2440, ITF2563 and ITF2955 glucuronide, and moxifloxacin in plasma:

- AUC_{0-t}: area under the concentration-time curve from time zero to the last measurable concentration
- AUC₀₋₁₂: area under the concentration-time curve from time zero to 12 hours
- AUC_{0-inf}: area under the concentration-time curve from time zero to infinity (extrapolated)
- C_{max}: maximum observed concentration
- Residual area: calculated as 100*(1- AUC_{0-t} / AUC_{0-inf})
- T_{max}: time of observed Cmax
- T_{½ el}: elimination half-life
- K_{el}: elimination rate constant
- CL/F: apparent total body clearance, calculated as Dose/AUC_{0-inf}
- Vd/F: apparent volume of distribution, calculated as Dose/K_{el} x AUC_{0-inf}

12.2 Urine PK Parameters

The following PK parameters will be calculated for ITF2357 and metabolites ITF2374, ITF2375, ITF2440, ITF2563 and ITF2955 glucuronide ITF2955 in urine:

- Ae_{0-t}: Cumulative urinary excretion from time zero to time t, calculated as the sum of the amounts excreted over each collection interval. The amount excreted in urine for each time interval is calculated as the urine concentration multiplied by the urine volume.
- R_{max}: Maximum rate of urinary excretion, calculated by dividing the amount of drug excreted in each collection interval by the time over which it was collected
- T_{Rmax}: Time of R_{max}, calculated as the midpoint of the collection interval during which R_{max} occurred

Clr: Renal clearance, calculated as Ae_{0-t} / AUC_{0-t} (plasma)

Additional PK analysis may be performed. Upon Sponsor's request, pharmacokinetic repeats might be performed according to Syneos Health's SOP. If re-assays are requested for pharmacokinetic reasons, final results will include re-assay values, while results with original values will be presented in an appendix of the clinical study report as supportive data.

12.3 Analysis Populations

12.3.1 Safety Population

The Safety Population will include all subjects who receive at least 1 dose of study drug (therapeutic and supratherapeutic doses of ITF2357, moxifloxacin, or placebo).

12.3.2 QT/QTc Population

The QT/QTc Population will include all subjects in the Safety Population with measurements at baseline as well as on-treatment with at least one post-dose time point with a valid Δ QTcF value. The QT/QTc Population will be used for the by-time point and categorical analyses of the cardiodynamic ECG parameters.

12.3.3 Pharmacokinetic Population

The PK population will include all subjects completing at least 3 periods, including at least T, ST, and M and for whom the PK profile can be adequately characterized. The pharmacokinetic population will be used for calculation of PK parameters and statistical analyses.

Any subject with pre-dose concentrations will be excluded from the PK and statistical analysis for the respective analyte for the concerned period if the pre-dose concentration is greater than 5% of the C_{max} value of that period for that subject.

Data from subjects who experienced emesis during the sampling interval and who were not withdrawn as per criterion established under section 9.14 may be evaluated after completion of the PK analysis.

Any subject who experienced emesis within 2 times median T_{max} of the current study will be excluded from the statistical analysis.

Data (concentrations and PK parameters) from subjects excluded due to a pre-dose concentration greater than 5% of their C_{max} or from subjects withdrawn due to adverse events or vomiting episodes will be presented but excluded from descriptive statistics for the concerned period.

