12.3.4 Pharmacokinetic Concentration Population

The PK concentration population will include all subjects who receive a dose of ITF2357 or moxifloxacin and provide at least one evaluable PK concentration for ITF2357 or moxifloxacin.

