12.3.5 PK/QTc Population

The PK/QTc Population will include all subjects who are in both the QT/QTc and PK Concentration populations with at least one pair of post-dose PK and QTcF data from the same time point as well as subjects in the QT/QTc population who received placebo. The PK/QTc Population will be used for the concentration-QTc analysis. PK/QTc Population will be defined for ITF2357 and for moxifloxacin.

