#### 6. Analysis Populations

Study populations will include: Safety population, QT/QTc population, Pharmacokinetic population, Pharmacokinetic concentration population and PK/QTc population.

When determining data availability for the study populations, the following aspects are to be considered (but not to be limited to) : inclusion and exclusion criteria, acceptable times for visit dates and measurements, compliance with treatment, the nature and quality of the data, withdrawal and any protocol deviation. Any decision for excluding data from the final data set will be provided with a detailed explanation and will be properly recorded and dated with Sponsor's approval. The final responsibility of deciding which subjects are to be included or excluded lies with the Investigator, and/or the Sponsor.

The analysis of safety and tolerability parameters will be based on the safety population detailed in Section 6.1 below. The analysis of cardiodynamic ECG parameters will be based the QT/QTc population detailed in Section 6.2 below. The analysis of PK parameters will be based on the PK population detailed in Section 6.3 below. PT/QTc population will be detailed in Section 6.4 below.

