### 6.3 Pharmacokinetic Population

The PK population will de defined as all subjects completing at least 3 periods, including at least Treatments T, ST, and M and for whom the PK profile can be adequately characterized. The PK population will be used for calculation of PK parameters and statistical analyses.

Any subject with pre-dose concentrations will be excluded from the PK and statistical analysis for the respective analyte for the concerned period if the pre-dose concentration is greater than 5% of the  $C_{max}$  value of that period for that subject.

Data from subjects who experienced emesis during the sampling interval and who were not withdrawn may be evaluated after completion of the PK analysis.

Data (concentrations and PK parameters) from subjects excluded due to a pre-dose concentration greater than 5% of their  $C_{max}$  or from subjects withdrawn due to adverse events or vomiting episodes will be presented but excluded from descriptive statistics for the concerned period.

Any subject who experienced emesis within 2 times median  $T_{max}$  of the current study will be excluded from the statistical analysis.

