#### Italfarmaco S.p.A.

#### 10.3 Analysis

#### 10.3.1 Concentration-QTc Analysis (Primary Analysis)

The relationship between plasma concentrations of ITF2357 and  $\triangle$ QTcF will be quantified using a linear mixed-effects modeling approach. The model will include  $\triangle$ QTcF as the dependent variable, plasma concentration of ITF2357 as the explanatory variate (0 for placebo), centered baseline QTcF (i.e., baseline QTcF for individual subject minus the population mean baseline QTcF for all subjects within the same treatment period) as an additional covariate, treatment (active = 1 or placebo = 0), time (i.e., nominal post-dose time point) as fixed effects, and random effects on intercept and slope per subject (Garnett et al).

An unstructured covariance matrix will be specified for the random effects. If convergence cannot be achieved even after appropriate rescaling of the concentrations, the random effect on the slope and intercept will be dropped, in this order, until convergence is achieved. The degrees of freedom (df) estimates will be determined by the Kenward-Roger method. From the model, the slope (i.e., the regression parameter for concentration ITF2357) and the treatment effect-specific intercept (defined as the difference between active and placebo) will be estimated together with the 2-sided 90% CL. The estimates for the time effects will be reported with df and SE.

The geometric mean of the individual  $C_{max}$  values for subjects in each of the active dose groups will be determined. The predicted effect and its 2-sided 90% CI for  $\Delta\Delta$ QTcF i.e., slope estimate × concentration + treatment effect-specific intercept) at this geometric mean  $C_{max}$  will be obtained. If the upper bound of the 2-sided 90% CI (equivalent to the upper bound of the 1-sided 95% CI) of the predicted QTc effect ( $\Delta\Delta$ QTcF is below 10 ms at clinically relevant plasma levels, it will be concluded that ITF2357 does not cause clinically relevant QTc prolongation within the observed plasma concentration ranges.

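### The PK Population requires T, ST and moxifloxacin all to be completed, which descriptive by-treatment PK summaries do not need, and no population is named for the geometric mean Cmax

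*Protocol*

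**What the plan says.** **Entry rule.** Protocol 12.3.3 defines the PK Population as "all subjects completing at least 3 periods, including at least T, ST, and M and for whom the PK profile can be adequately characterized". SAP 6.3 has the same rule: "all subjects completing at least 3 periods, including at least Treatments T, ST, and M and for whom the PK profile can be adequately characterized".

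**Use.** Protocol 12.3.3: "The pharmacokinetic population will be used for calculation of PK parameters and statistical analyses". SAP 6: "The analysis of PK parameters will be based on the PK population detailed in Section 6.3 below". Cmax is one of the listed parameters (Protocol 12.1, SAP 11.3.1). Protocol 12.4.2 plans descriptive PK statistics only, with no inference.

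**Other exclusions in the same section.** The pre-dose concentration rule works by analyte and period. Data from subjects withdrawn for adverse events or vomiting are shown but left out of the descriptive statistics for the period concerned.

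**Primary model.** Protocol 12.3.5: "The PK/QTc Population will be used for the concentration-QTc analysis". That set is built on the PK Concentration Population, "all subjects who receive a dose of ITF2357 or moxifloxacin and provide at least one evaluable PK concentration for ITF2357 or moxifloxacin", and is defined separately for ITF2357 and moxifloxacin. No completed moxifloxacin period is needed.

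**Prediction step.** SAP 10.3.1 takes "The geometric mean of the individual" Cmax values in each active dose group and reads the predicted ΔΔQTcF there against 10 ms. SAP 10.4 does the same for moxifloxacin against 5 ms. Neither section, nor Protocol 12.4.1, says which population supplies those Cmax values.

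**Assay scope.** Protocol section 10 has samples assayed for the PK Population and for subjects withdrawn because of adverse events or vomiting. Protocol 9.9.1 and SAP 10.1 have ITF2357 measured in all subjects given it.

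**The concern.** The PK objective is to describe ITF2357 at 100 mg and 300 mg. A mean or geometric mean for one dose needs only the subjects with a usable profile on that dose. The entry rule nevertheless makes each profile depend on two other treatments. A subject with complete T and ST profiles who never takes moxifloxacin drops out of the ITF2357 tables, and a subject with a good moxifloxacin profile drops out if either ITF2357 dose is missing.

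Completion can also depend on treatment. Protocol 9.14 lists safety reasons, vomiting within 4 hours of dosing and marked QT/QTc prolongation among the grounds for withdrawal. If any of these follows exposure, a summary restricted to subjects who finished T, ST and M describes a selected group.

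The link to the QT decision is Cmax. The model may be fitted to more subjects than supply the concentration at which it is evaluated. Because the population for that step is unnamed, two analysts could report different predictions from the same fit.

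**Working it through.** **The plan's own figure.** Protocol 8.1 and SAP 3.5 enrol up to 34 to obtain 28 evaluable: 34 − 28 = 6, or 6/34 = 17.6%. The sample-size rationale is not visible in the public text, so 28 cannot be recomputed. The visible text does not define evaluable; below, the 28 are assumed to complete all four periods.

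**Which profiles the rule removes.** Each of the 12 sequences (Protocol 9.4, SAP Table 1) was cut off after Period 1, 2 or 3.

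| Exit after | Sequences excluded | T lost | ST lost | M lost | Active profiles lost per leaver |
|---|---|---|---|---|---|
| Period 1 | 12 of 12 | 3 | 3 | 3 | 9/12 = 0.75 |
| Period 2 | 12 of 12 | 6 | 6 | 6 | 18/12 = 1.5 |
| Period 3 | 9 of 12 | 6 | 6 | 6 | 18/12 = 1.5 |

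Sequences 2, 7 and 12 end with placebo, so a subject leaving after Period 3 stays in. T and ST are both complete, with only M standing between the subject and inclusion, in sequences 1 and 7 after Period 2 and in 1, 5 and 9 after Period 3: 5 of 36 cells.

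**Expected loss.** Assumption: 6 leavers spread evenly over the 36 sequence-by-exit cells.

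- Active profiles: 6 × (9 + 18 + 18)/36 = 7.5
- ST profiles: 6 × (3 + 6 + 6)/36 = 2.5, and the same for T and for M
- Subjects with both T and ST complete, lost solely for missing M: 6 × 5/36 = 0.83
- Leavers who stay in: 6 × 3/36 = 0.5, so the PK Population is 28.5

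**Effect on the ST geometric mean Cmax, if it were taken from the PK Population.** Let r be the geometric mean Cmax of the removed subjects divided by that of the retained ones. The documents give no value; 0.7 to 2.0 is an assumed range. The geometric mean with the profiles restored, divided by the PK Population value, is r^f, where f is the restored share.

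| r | Even spread, f = 2.5/31 = 0.081 | All 6 leavers have an ST profile, f = 6/34 = 0.176 |
|---|---|---|
| 0.7 | 0.972 | 0.939 |
| 1.0 | 1.000 | 1.000 |
| 1.5 | 1.033 | 1.074 |
| 2.0 | 1.057 | 1.130 |

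For the 0.83 subjects lost solely for missing M, f = 0.83/29.3 and 1.5^f = 1.012, about 1.2%.

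**In milliseconds.** The prediction is slope × Cmax + intercept, so only the slope part scales. For an illustrative slope part of 10 ms and r = 1.5, the shift is 10 × 0.033 = 0.33 ms under even spread and 10 × 0.012 = 0.12 ms for the missing-M losses alone. Over r from 0.7 to 2.0 with even spread it runs from −0.28 to +0.57 ms.

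**The case against.** **Common-set design.** Using the same subjects for every treatment is a legitimate choice in a crossover, and PK is secondary and descriptive. This stands as a reason to rank the point modestly. It does not justify the rule, since no planned PK comparison uses the common set.

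**The text is softer than the entry rule.** Parameters from adverse-event or vomiting withdrawals are still presented, and their exclusion from the statistics is by period. SAP 11.4 keeps a parameter available for only one period in the descriptive statistics. So it would be wrong to say that every leaver contributes nothing. But neither passage overrides the entry rule: SAP 11.4 may refer only to members of the PK Population whose parameter could not be derived in other periods, and a subject who leaves for another reason, such as withdrawn consent, is not covered by the presentation sentence.

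**A reader might infer that the primary prediction uses a Cmax from completers only and is biased downward.** The documents do not support this. The prediction step names no population and belongs to an analysis assigned to the PK/QTc Population. The inference is plausible, because Cmax is a PK parameter and PK parameters are assigned to the PK Population, but it remains an inference. Completers is also the wrong word, since a subject missing only placebo is kept. The direction is not fixed either: the shift can be up, down or nil.

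**A reader might also infer that a missing moxifloxacin period removes ITF2357 data from the primary model.** The population definitions say otherwise. It could happen only if Protocol section 10 were followed literally, leaving unassayed the samples of someone who missed moxifloxacin for a reason other than an adverse event or vomiting. Protocol 9.9.1 and SAP 10.1 contradict that reading.

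**Conclusion.** The point holds for the PK summaries. The entry rule discards valid profiles that no planned analysis requires it to discard: about 7.5 active profiles for 6 evenly spread leavers, 2.5 of them ST, with 0.83 subjects losing both ITF2357 profiles solely for a missing moxifloxacin period. The cell counts follow from the sequence table; the totals rest on the even spread and on reading 34 − 28 as leavers.

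For the primary analysis and assay sensitivity, the defect is an unnamed population, not a stated restriction. If the PK Population were used, restoring the removed profiles would change the ST geometric mean Cmax by −2.8% to +5.7% under even spread, and by −6.1% to +13.0% if all 6 leavers had an ST profile, over the assumed range of r. There is no change if leaving is unrelated to exposure. The slope and intercept come from the wider set, provided all samples are assayed. This could affect the conclusion only if the confidence bound lay close to its threshold. The wording should be corrected; nothing here shows that the primary result would be wrong.

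**What to change.** 1. In Protocol 12.3.3 and SAP 6.3, define the PK Population separately for each treatment and analyte: every subject who received that treatment and whose profile for that analyte in that period is adequate for deriving the parameters. Delete the condition on completing three periods with T, ST and M among them. Keep the pre-dose and emesis exclusions, applied to the period concerned.
2. In Protocol 12.4.1 and SAP 10.3.1 and 10.4, state that the geometric mean Cmax uses every subject in the relevant PK/QTc Population with an evaluable Cmax on that treatment.
3. Reconcile Protocol section 10 with Protocol 9.9.1 and SAP 10.1 so that ITF2357 is assayed in all subjects dosed with it. Without this, the second change could fail for want of data.
4. Align SAP 11.4, on parameters available for one period only, with the revised SAP 6.3.

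The cost is protocol and SAP wording, with no new data collection. The number of subjects will differ slightly between treatments in the PK tables; it already differs between analytes, because metabolites are measured in only 12 subjects.
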